#### **9.3.1 Stopping Rules**

For the second, third, and fourth interim analysis, the primary endpoint will be assessed for futility by the DSMB. Enrollment will be stopped if the conditional power is  $<10\%$  based on the percentage of subjects classified in categories 4 through 8 on the 8-point WHO Ordinal Clinical Scale for RBT-9 versus placebo.

Efficacy will be declared at the fourth interim analysis if the conditional power is  $>80\%$  (with all subjects followed through Day 28). If efficacy is declared, the DSMB will advise regarding study continuation.

## **9.4 Recordkeeping and Monitoring**

All subject data will be reported in the electronic data capture (EDC) system. All original source documents should be available for periodic monitoring and/or retrieval by a Sponsor representative designee. The Investigator is responsible for the accuracy of all data entered in the electronic case report forms (eCRFs) and for the timely completion of the eCRFs. The supporting documentation will be maintained at the site for a minimum of either:

1. Two (2) years following the approval of RBT-9 for this indication by the Food and Drug Administration (FDA)

**or**

2. Two (2) years following notification by Sponsor to the FDA of the termination of the entire investigation.

The Sponsor must be contacted and give written authorization prior to any study records being destroyed at investigative sites.

This study will be conducted in compliance with Good Clinical Practice (GCP), which includes the Sponsor- and IRB-approved protocol and ICF and the FDA and International Conference on Harmonisation (ICH) regulatory guidelines and requirements. No changes will be made without prior approval unless it is imperative for subject safety. Any such departures from the protocol will be reported immediately to the Sponsor and relevant IRB.

All subjects' medical records and study-related documents will be made available to the Sponsor for regular monitoring and audits as well as to the IRB and FDA or other governmental agency with oversight or compliance responsibilities for assuring subject rights and welfare.

## **9.5 Investigational Supplies**

Subjects will be randomly assigned in a 2:1 ratio to receive a single dose of open-label RBT-9 (90 mg) or placebo administered intravenously over a 120-minute period on Day 1.

The proposed dose is based on previous human studies with RBT-9 and preclinical pharmacology and toxicology data. The selected dose was determined to be optimal for safely and maximally increasing biomarkers of cytoprotection within 24 to 48 hours, with effects lasting for at least 7 days.

### **9.5.1 Study Drug Description**

The active investigational product is a mixture of RBT-9 (stannous protoporphyrin) in a solution of sodium chloride.

Commercially available 0.9% sodium chloride for injection will be used for placebo administration at study sites.

### **9.5.2 Packaging**

RBT-9 is supplied as a sterile liquid for intravenous injection at a concentration of 9 mg/mL in 5-mL glass vials that are protected from light. Thus, each vial contains 45 mg of RBT-9.

Following receipt of Form FDA 1572 and IRB approval for a given site, RBT-9 will be sent to the study site.

### **9.5.3 Investigational Product Dispensing**

All investigational products will be dispensed by designated and trained site pharmacy staff.

### **9.5.4 Dosage Preparation and Administration**

Instructions for dose preparation will be specified in the Pharmacy Manual. RBT-9 (90 mg; 2 vials) or placebo will be administered as an intravenous infusion over a 120-minute period under the supervision of the Investigator/study staff.

### **9.5.5 Storage Requirements**

RBT-9 should be stored at controlled room temperature conditions (defined as 20 - 25°C/68 - 77°F with excursions of <24 consecutive hours permitted between 15 - 30°C/59 - 86°F) and protected from light.

### **9.5.6 Investigational Product Accountability**

The Investigator or designee is responsible for maintaining accurate records accounting for the receipt, dispensing, and final disposition of all investigational products using the appropriate investigational product logs provided by the Sponsor.

### **9.5.7 Retrieval and Destruction**

Periodically throughout the study, the site will perform investigational product reconciliation on a per-subject basis. The Sponsor's site monitor will review the log and once any discrepancies have been resolved, authorize destruction/disposition of the supplies associated with a given subject by signing the reconciliation log and will witness the destruction/disposition.

## **9.6 Randomization and Blinding**

Each subject will be assigned an identification number by the site after the subject provides written informed consent.

The identification number will consist of a 7-digit number:

- The first 4 digits will designate the site number as assigned by the Sponsor.
- The last 3 digits will designate the order of the subject at that site.

The first subject who signs the ICF at the site is assigned the identification number 001, the second subject who signs the ICF is assigned 002, the third is assigned 003, etc. The subject will maintain the same identification number throughout the entire study. If a subject signs the ICF but does not meet the inclusion/exclusion criteria, the subject will

be marked as a screen fail on the Screening and Enrollment Log provided by the Sponsor and will be entered in the EDC system as a screen failure.

If the subject qualifies for study entry after Screening, the site staff will access the Interactive Response Technology (IRT) system and enter responses regarding the subject's time since COVID-19 diagnosis (<48 hours,  $\geq$ 48 hours). The system will then provide the subject's open-label treatment assignment (RBT-9 or placebo) according to the randomization code.

## 9.7 Study Phase

### 9.7.1 Screening (Within 24 Hours Prior to Dosing)

Study candidates will be evaluated for study entry according to the stated inclusion and exclusion criteria ([Sections 9.1](#) and [9.2](#), respectively). The following procedures will be performed during Screening to establish each candidate's eligibility for enrollment into the study:

- Obtain signed, written informed consent. The informed consent must be signed before any procedures are performed.
- Record demographic information. The subject should also provide phone/email information for themselves and their closest relative so they can be contacted for virtual visits.
- Record medical history, including documentation of COVID-19 infection.
- Record COVID-19 signs and symptoms.
- Record concomitant medications, including previous treatment with anti-IL-6 therapies or Remdesivir.
- Perform physical examination, including calculation of body mass index.
- Record vital signs (blood pressure, pulse rate, SpO2, FiO2, and temperature).
- Obtain urine sample for pregnancy testing for female subjects of childbearing potential.
- Obtain blood samples for clinical chemistry, hematology, and troponin I testing.
- Obtain urine sample for urinalysis.
- Assess the severity of COVID-19 using the 8-point WHO Ordinal Clinical Scale (see [Section 9.10.5](#)).

The Investigator will evaluate the results of all examinations, including clinical laboratory tests, and determine each candidate's suitability for the study according to the eligibility criteria.

### 9.7.2 Day 0/1 (Within 24 Hours of Screening)

Once a candidate is determined to be eligible for the study, the following procedure will be performed.

- Access the IRT system to obtain the subject's randomized treatment assignment (see [Section 9.6](#)).

No more than 24 hours can elapse between screening and dosing with RBT-9.

After the subject's randomized treatment is obtained through the IRT system, study drug administration will be performed as follows:

- Study drug will be administered as an infusion over a 120-minute period under the supervision of the Investigator/study staff. The date, rate of infusion, total infusion volume, and start and stop times of dosing will be recorded.

### **9.7.3 Day 1 (Post-Dose)**

- Record COVID-19 signs and symptoms.
- Record COVID-19 complications.
- Record vital signs.
- Record severity of COVID-19.
- Solicit any adverse events.

### **9.7.4 Visit Days ( $\pm 1$ ) 7, 14, 21, and 28/EOF**

All subjects will be assessed for the procedures listed below. For subjects who have been discharged from the hospital, visits will be conducted virtually (eg, by phone or video contact) on Days ( $\pm 1$ ) 7, 14, and 21. The visit on Day 28 should be conducted in person, but may be conducted virtually.

- Record COVID-19 signs and symptoms.
- Record COVID-19 complications.
- Record changes in concomitant medication.
- Perform physical examination, which will be symptom-directed visual inspection.
- Record vital signs.
- Assess the severity of COVID-19 using the 8-point WHO Ordinal Clinical Scale (see [Section 9.10.5](#))
- Obtain blood samples for clinical chemistry and hematology testing (Day 28 only).
- Obtain urine sample for urinalysis (Day 28 only).
- Solicit any adverse events.

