- 6 Severity of COVID-19 will be assessed by the 8-point WHO Ordinal Clinical Scale, which includes: 1. Ambulatory (not hospitalized), no limitation of activities; 2. Ambulatory (not hospitalized), limitation of activities; 3. Hospitalized, no oxygen therapy; 4. Hospitalized, oxygen by mask or nasal prongs; 5. Hospitalized, non-invasive ventilation or high-flow oxygen; 6. Hospitalized, intubation and mechanical ventilation; 7. Hospitalized, ventilation plus additional organ support – vasopressors (pressors), renal replacement therapy (RRT), extracorporeal membrane oxygenation (ECMO); 8. Death. The Ordinal Clinical Scale is the clinical status at the first assessment of a given study day.
- 7 Parameters include: total protein, albumin, bicarbonate, blood urea nitrogen, serum creatinine, total bilirubin, alkaline phosphatase, glucose, sodium, potassium, phosphorus, calcium, magnesium, gamma-glutamyl transferase, alanine aminotransferase, aspartate aminotransferase, and ferritin.
- 8 Clinical chemistry and hematology are optional on Day 28.
- 9 Parameters include: hemoglobin, hematocrit, leukocytes with differential (absolute), and platelets.
- 10 Parameters include pH, specific gravity, protein, glucose, nitrite, ketones, WBC esterase, and occult blood.
- 11 Administer study drug after all pre-dose evaluations have been completed.
- 12 Adverse events that are ongoing on Day 28 will be followed on Day 42; adverse events that are ongoing on Day 42 will be followed on Day 56.
- 13 Safety follow-up assessment will be conducted virtually by telephone or video contact to determine the following: hospitalization status (hospitalized: yes, no), intubation status (intubated: yes, no), and survival (alive: yes, no).

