### **9.3 Study Design**

This is a Phase 2, randomized, placebo-controlled, multicenter study that will evaluate the efficacy, tolerability, and safety of a single dose of RBT-9 on the progression of COVID-19 infection in non-critically ill adults who are at high risk due to age and/or comorbid conditions. Subjects with documented SARS-CoV-2 infection who are at high risk for disease progression, as defined in the inclusion criteria (see [Section 9.1](#)), and require observation and/or treatment in a hospital will be screened for entry into the study. Eligible subjects will be stratified by time since COVID-19 diagnosis (<48 hours,  $\geq$ 48 hours) and randomly assigned in a 2:1 ratio to receive a single intravenous infusion of 90 mg RBT-9 or placebo (normal saline). No more than 24 hours can elapse between Screening and Dosing of RBT-9.

All subjects will be assessed through Day 56. All subjects, regardless of hospitalization status, will be assessed on Days 7, 14, 21, and 28, according to the Event Schedule (see [Section 5.1](#)). Assessments will include severity of COVID-19 measured by the 8-point WHO Ordinal Clinical Scale, physical examination, vital signs, clinical laboratory evaluations, concomitant medications, and adverse events. For subjects who have been discharged from the hospital, visits on Days 7, 14, and 21 will be conducted virtually (eg, by telephone or video contact). The Day 28 visit should be conducted in person, but may be conducted virtually, as well. Subjects will also be assessed at safety follow-up visits, which will be conducted virtually (eg, by telephone or video contact) on Days 42 and 56.

An independent data and safety monitoring board (DSMB) will actively monitor interim data to make recommendations regarding study conduct/continuation. The DSMB will meet once the first 30 subjects complete the Day 7 assessment to perform the first interim analysis of the safety data. Enrollment of 30 additional subjects will proceed if the safety profile of RBT-9 is deemed acceptable (as determined by the DSMB). Two additional DSMB interim analyses will be performed once 60 and 90 subjects complete the Day 7 evaluation. The last DSMB interim analysis will be performed once 150 subjects complete the Day 28 evaluation; sample size re-estimation will also be performed to allow a sample size increase to 252 subjects based on pre-defined conditional power rules.

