#### **11.1 Endpoints**

The following efficacy endpoints are defined for the study.

Primary Endpoint: Percentage of subjects in each treatment group in categories 4 through 8 of the 8-point WHO Ordinal Clinical Scale through Day 28.

Secondary Endpoints:

- Time to first occurrence of either death from any cause or new/worsened organ dysfunction through Day 28, defined as at least one of the following:
  - Respiratory decompensation
  - New or worsening congestive heart failure
  - Requirement of vasopressor therapy and/or inotropic or mechanical circulatory support
  - Ventricular tachycardia or fibrillation lasting at least 30 seconds and/or associated with hemodynamic instability or pulseless electrical activity, or resuscitated cardiac arrest

- Initiation of renal replacement therapy.
- Percentage of subjects who are alive at Day 28.
- Among subjects who begin oxygen therapy, mean change from initiation to last day on oxygen or Day 28 (whichever happens first) in SpO2/FiO2 ratio.
- Percentage of subjects with fever through Day 28.
- Percentage of subjects who develop AKI, as determined by the Investigator, through Day 28.
- Percentage of subjects with new or worsening congestive HF through Day 28.
- Percentage of subjects with ventricular tachycardia or fibrillation lasting at least 30 seconds and/or associated with hemodynamic instability or pulseless electrical activity, or resuscitated cardiac arrest through Day 28.
- Percentage of subjects who remain hospitalized at Day 28.
- Length of hospitalization through Day 28.
- Number of oxygen-free days through Day 28.
- Percentage of subjects transferred to the ICU through Day 28.
- Number of days on mechanical ventilation through Day 28.
- Time to and duration of vasopressor or inotrope utilization through Day 28.
- Percentage of subjects who begin dialysis through Day 28.

Exploratory Endpoints:

- Duration of COVID-19 symptoms through Day 56

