#### **11.5 Analysis of Safety Endpoints**

Safety measures including adverse events, clinical laboratory tests, vital signs, and concomitant medication usage will be summarized descriptively by treatment group.

The principle of treatment emergence will be employed for the analysis of adverse event data. A treatment-emergent adverse event is defined to be any event that occurs during the observation period of the study and was not present at baseline, or exacerbation of a condition present at baseline.

Treatment-emergent adverse events will be classified by the Medical Dictionary for Regulatory Activities. The type, incidence, timing (onset, duration), relationship, and severity will be reported for all adverse events. Reasons for withdrawal due to adverse events will also be reported.

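### No post-dose chemistry or hematology result is required and none is scheduled in the first week, so the DSMB reviews triggered at Day 7 may see few laboratory values and AKI detection follows routine care

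*Combined protocol and SAP*

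**What the plan says.** Blood is taken before dosing. Section 9.7.1 reads "Obtain blood samples for clinical chemistry, hematology, and troponin I testing". The Day 1 post-dose list (9.7.3) contains no laboratory test. For Days 7 to 28, Section 9.7.4 reads "Obtain blood samples for clinical chemistry and hematology testing (Day 28 only", and the same section allows the Day 28 visit to be virtual. Footnote 8 of the Event Schedule (5.1) adds "Clinical chemistry and hematology are optional on Day 28". Urinalysis is also confined to that visit ("Obtain urine sample for urinalysis (Day 28 only"), but no footnote makes it optional.

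Section 9.3 lists "physical examination, vital signs, clinical laboratory evaluations, concomitant medications, and adverse events" among the assessments, and says they follow the Event Schedule. Section 9.9 likewise makes the Event Schedule the source for collection times.

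Three parts of the plan depend on these results:

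- DSMB reviews: "The DSMB will meet once the first 30 subjects complete the Day 7 assessment to perform the first interim analysis of the safety data" (9.3). Two further reviews come when 60 and 90 subjects complete Day 7, and the last when 150 complete Day 28.
- A secondary endpoint: "Percentage of subjects who develop AKI, as determined by the Investigator, through Day 28" (11.1). No creatinine or urine-output criterion is given, and Section 10.5 states that the study is open-label.
- Safety reporting: "Safety measures including adverse events, clinical laboratory tests, vital signs, and concomitant medication usage will be summarized descriptively by treatment group" (11.5). Section 11.3 rules out imputation.

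Sections 9.10.5 and 9.10.6 ask sites to document COVID-19 signs and complications, including laboratory abnormalities, on Days 7, 14, 21 and 28. They also say that new or worsening ones are not to be reported as adverse events or serious adverse events.

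**The concern.** The gap falls where the protocol expects the drug to act. Section 6.2 describes an immediate stress response that turns within 24 to 48 hours, and Section 9.5 describes biomarker effects lasting at least 7 days. No blood is scheduled in that window. Enrollment of the second 30 subjects depends on the DSMB finding the safety profile acceptable at the first review, yet nothing in the schedule ensures that a post-dose creatinine, liver enzyme or blood count is in front of it.

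The adverse-event route does not reliably fill the gap. Section 6.1 names acute kidney injury among the complications of COVID-19. A creatinine rise after the infusion may therefore go unsampled, or be found in routine care and recorded as a complication rather than as an adverse event.

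AKI has a related difficulty. Without scheduled creatinine, a case is found when someone has a clinical reason to test, which is more likely in hospital than after discharge. Length of hospitalization is itself an endpoint, and the person deciding whether AKI occurred knows the treatment. Organ protection is part of the drug's rationale (6.2, 6.3), so an artefact in this endpoint could be read as support for it.

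**Working it through.** The plan states no figure on this point, so there is nothing to reproduce. The check sets the sections side by side and then asks what the DSMB could hold.

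**1. Required post-dose bloods per subject**

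| Time | Chemistry and hematology | Source |
|---|---|---|
| Screening | Scheduled | 9.7.1 |
| Day 1 post-dose | None | 9.7.3 |
| Days 7, 14, 21 | None | 9.7.4 |
| Day 28 | Listed without qualification in 9.7.4; optional in footnote 8 | 9.7.4, 5.1 |
| Days 42, 56 | None | 9.8.1 |

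If footnote 8 governs, the number of required post-dose draws is 0. If 9.7.4 governs, it is 1, at Day 28. On either reading, the number scheduled in the first week is 0.

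**2. What reviews 1 to 3 could hold**

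With 2:1 allocation, the expected number on RBT-9 is n × 2/3: 30 × 2/3 = 20, 60 × 2/3 = 40, 90 × 2/3 = 60. None of these subjects has a scheduled first-week blood result.

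Earlier enrollees may already have reached Day 28. From Day 7 to Day 28 is 21 days, or 3 weeks. With uniform accrual of r per week, the number at Day 28 when subject n reaches Day 7 is max(0, n − 3r), ignoring visit windows. The accrual rate is not in the documents, so r is an assumption shown over a range:

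| Review | r = 2 | r = 5 | r = 10 | r = 20 | r = 30 |
|---|---|---|---|---|---|
| n = 30 | 24 | 15 | 0 | 0 | 0 |
| n = 60 | 54 | 45 | 30 | 0 | 0 |
| n = 90 | 84 | 75 | 60 | 30 | 0 |

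For example, n = 30 and r = 5 gives 30 − 15 = 15. These are upper limits on the Day 28 results available, because the draw is optional and the visit may be virtual.

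**3. AKI ascertainment**

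Let p be the true AKI rate, h the share of cases arising in hospital, and s_H and s_D the detection probabilities in hospital and after discharge. Then

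observed rate = p × [h·s_H + (1 − h)·s_D].

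With the same p, s_H and s_D in both arms, the apparent risk ratio is

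[h_R·s_H + (1 − h_R)·s_D] / [h_P·s_H + (1 − h_P)·s_D],

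where R is RBT-9 and P is placebo. The true rate cancels. If h_R = h_P, the ratio is 1. If detection is better in hospital (s_H > s_D) and fewer RBT-9 cases arise there, the ratio falls below 1 with no true effect; if more do, it rises above 1. The documents give none of h, s_H or s_D, so the formula gives a direction but no size.

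**The case against.** The strongest reply is that laboratory findings do have a way into the database. Sections 9.10.5 and 9.10.6 cover laboratory abnormalities on four visit days, 9.7.3 records complications on Day 1, and 9.4 sends all subject data to the EDC system. Section 10.2 allows an abnormal laboratory finding to be an adverse event, and 10.1 requires serious adverse events to be reported within 24 hours. Screening values exist, and under slow accrual many earlier enrollees could have Day 28 results. The laboratory manual and any DSMB charter are not among the documents and could add more. All of this stands. A reader might infer that the Day 7 reviews have no laboratory data at all, or cannot detect organ toxicity; the documents do not support that. The recording route is nevertheless unsystematic: it captures abnormalities that someone happened to test for, not values with a denominator.

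A reader might also infer that Section 9.3 contradicts the schedule by listing laboratory evaluations for Days 7 to 28. It defers to the Event Schedule in the same paragraph, so the list is loose wording. The real disagreement is between 9.7.4 and footnote 8.

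Finally, it is tempting to say that the AKI comparison is biased, or to attach a risk ratio to it. Bias between arms needs hospital stay or testing to differ by arm. Any ratio would only restate the assumed hospital shares and detection rates. Outpatient tests, readmission or the optional Day 28 draw could also reveal a case.

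Optional bloods and virtual visits are understandable choices for a single-dose Phase 2 study in a pandemic, and the primary endpoint uses no laboratory value. That limits the seriousness but does not answer the point about safety data.

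**Conclusion.** The point holds in this form: no post-dose chemistry or hematology result is required if footnote 8 governs, and none is scheduled in the first week on any reading. The DSMB reviews at 30, 60 and 90 subjects have no scheduled first-week bloods for about 20, 40 and 60 RBT-9 subjects. What else they hold depends on accrual, on uptake of an optional draw and on local practice. The by-arm laboratory summaries may contain few post-dose values. AKI detection follows routine care and could differ between arms, by an amount the documents cannot supply.

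This should be fixed because first-week results that are not captured may not be recoverable later and the remedy is cheap. It does not threaten the primary analysis. The conclusion rests on the protocol text alone; a laboratory manual or DSMB charter that already requires these data would narrow it.

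**What to change.** 1. In 5.1 and 9.7.4, have sites enter in the eCRF, with dates, the creatinine, ALT/AST, bilirubin and blood-count results already obtained in routine care from Day 1 through Day 28, including readmissions and outpatient tests where available. Give these to the DSMB by arm at each review.
2. Reconcile footnote 8 with 9.7.4 by making Day 28 chemistry and hematology required for subjects who are in hospital or seen in person.
3. Report by arm the number of subjects with any post-dose creatinine. Beside the investigator's determination, add a programmed creatinine-based AKI analysis as a sensitivity analysis, with its criterion fixed in advance. State two limits with it. Screening creatinine may already be raised, because exclusion 3 (9.2) admits AKI due to pre-renal azotemia or urinary tract obstruction. Ascertainment after discharge remains incomplete, so this analysis exposes an imbalance in testing but does not remove it.

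The cost is a protocol amendment, extra data entry of results already in the chart, and a Day 28 draw in some subjects for whom it would have been skipped. No visits are added.
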